7.4.4.3 Management of neutropenia, leukopenia and thrombocytopenia

Table 9 Management of neutropenia, leukopenia and thrombocytopenia

Toxicity	Study treatment dose adjustment
CTCAE Grade 1-2	Investigator judgement to continue treatment or if dose interruption, this should be for a maximum of 4 weeks; appropriate supportive treatment and causality investigation
CTCAE Grade 3-4	Dose interruption until recovered to CTCAE gr 1 or better for a maximum of 4 weeks. If repeat CTCAE grade 3-4 occurrence, dose reduce olaparib to 250 mg twice daily as a first step and 200 mg twice daily as a second step

Adverse event of neutropenia and leukopenia should be managed as deemed appropriate by the investigator with close follow up and interruption of study drug if CTC grade 3 or worse neutropenia occurs.

Primary prophylaxis with Granulocyte colony-stimulating factor (G-CSF) is not recommended, however, if a patient develops febrile neutropenia, study treatment should be stopped and appropriate management including G-CSF should be given according to local hospital guidelines. Please note that G-CSF should not be used within at least 24 h (7 days for pegylated G-CSF) of the last dose of study treatment unless absolutely necessary.

Platelet transfusions, if indicated, should be done according to local hospital guidelines.

For cases where patients develop prolonged haematological toxicity (≥ 2 week interruption/delay in study treatment due to CTC grade 3 or worse), refer to guidance later in this section for the management of this.

7.4.4.4 Management of prolonged haematological toxicities while on study treatment

If a patient develops prolonged haematological toxicity such as:

- ≥ 2 week interruption/delay in study treatment due to CTC grade 3 or worse anaemia and/or development of blood transfusion dependence
- ≥ 2 week interruption/delay in study treatment due to CTC grade 3 or worse neutropenia ($ANC < 1 \times 10^9/L$)
- ≥ 2 week interruption/delay in study treatment due to CTC grade 3 or worse thrombocytopenia and/or development of platelet transfusion dependence (Platelets $< 50 \times 10^9/L$)

Check weekly differential blood counts including reticulocytes and peripheral blood smear. If any blood parameters remain clinically abnormal after 4 weeks of dose interruption, the patient should be referred to haematologist for further investigations. Bone marrow analysis and/or blood cytogenetic analysis should be considered at this stage according to standard

Clinical Study Protocol - 6
Olaparib - ESR-18-13807

haematological practice. Study treatment should be discontinued if blood counts do not recover to CTC gr 1 or better within 4 weeks of dose interruption.

Development of a confirmed myelodysplastic syndrome or other clonal blood disorder should be reported as an SAE and full reports must be provided by the investigator to AstraZeneca Patient Safety. Olaparib treatment should be discontinued if patient's diagnosis of MDS and/or AML is confirmed.

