3. STUDY DESIGN

3.1 Overall design

This is a pilot, multi-center study evaluating the prevalence and timing of folate deficiency in patients with advanced solid tumors who are eligible to receive olaparib.

If patients develop folate deficiency concomitantly with a Hgb less than 12.0 g/dl (grade 1), they will then be randomized to receive either a placebo or folate supplementation.

All randomized patients who develop a Hgb less than 10 g/dl (grade 2) concomitantly with folate deficiency will receive folic acid supplementation irrespective of their prior randomization. If such patients were originally randomized to receive folic acid and continue to have a Hgb less than 10 g/dl and folate deficiency despite folate supplementation, folic acid dose will be increased to 2 mg daily or higher at the discretion of the investigator.

Patients will continue with olaparib until objective disease progression (determined by treating physician assessment) as long as in the Investigator's opinion they are benefiting from treatment and they do not meet any other discontinuation criteria.

For an overview of the study design see Figure 1, Section 1.3. For details on treatments given during the study, see Section 5.1 Treatments Administered.

For details on what is included in the efficacy and safety endpoints, see Section 2 Objectives and Endpoints.

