7.4.4.1 Management of haematological toxicity

7.4.4.2 Management of anaemia

Table 8 Management of anaemia

Haemoglobin	Action to be taken
Hgb < 10 but ≥ 8 g/dl (CTCAE Grade 2)	
First occurrence: Give appropriate supportive treatment and investigate causality. Investigator judgement to continue olaparib with supportive treatment (e.g., transfusion) or interrupt dose for a maximum of 4 weeks. Study treatment can be restarted if Hb has recovered to > 9g/dl.
 
Subsequent occurrences: If Hgb < 10 but ≥ 9 g/dl investigator judgement to continue olaparib with supportive treatment (e.g., transfusion) or dose interrupt (for max of 4 weeks) and upon recovery dose reduction may be considered (to 250 mg twice daily as a first step and to 200 mg twice daily as a second step). If Hgb < 9 but ≥ 8 g/dl, dose interrupt (for max of 4 weeks) until Hb ≥ 9 g/dl and upon recovery dose reduction may be considered (to 250 mg twice daily as a first step and to 200 mg twice daily as a second step).

Hgb < 8 g/dl (CTCAE Grade 3)	
Give appropriate supportive treatment (e.g., transfusion) and investigate causality. Interrupt olaparib for a maximum of 4 weeks until improved to Hgb ≥ 9 g/dl. Upon recovery dose reduce to 250 mg twice daily as a first step and to 200 mg twice daily as a second step in the case of repeat Hgb decrease.

Common treatable causes of anemia (e.g., iron, vitamin B12 or folate deficiencies and hypothyroidism) should be investigated and appropriately managed. In some cases management of anemia may require blood transfusions. For cases where patients develop prolonged haematological toxicity (≥2 week interruption/delay in study treatment due to CTC grade 3 (Hgb less than 8.0 g/dl) or worse anemia and/or development of blood transfusion dependence), refer to guidance later in this section for the management of this.

Clinical Study Protocol - 6
Olaparib - ESR-18-13807

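### Table 8 and section 7.4.4.4 give opposite olaparib instructions for a patient still held at week 4 for grade 3 anaemia with haemoglobin 9.0 to 9.9 g/dl

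*Combined protocol and SAP*

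**What the plan says.** Table 8 (section 7.4.4.2) deals with anaemia by haemoglobin level. In the grade 3 row, for haemoglobin below 8 g/dl, it says: "Interrupt olaparib for a maximum of 4 weeks until improved to Hgb ≥ 9 g/dl". After recovery, treatment resumes at a reduced dose. In the grade 2 row, for a first occurrence, it says: "Study treatment can be restarted if Hb has recovered to > 9g/dl". Later grade 2 occurrences below 9 g/dl use at least 9 g/dl.

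The text under Table 8 sends prolonged cases to guidance later in the section. It does not say what then happens to the 9 g/dl level.

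Section 7.4.4.4 is that guidance. For anaemia, its trigger is a hold of at least two weeks for grade 3 or above, or dependence on transfusion, or both. It ends with: "Study treatment should be discontinued if blood counts do not recover to CTC gr 1 or better within 4 weeks of dose interruption".

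The protocol also fixes the grades. Table 8 labels its milder row "Hgb < 10 but ≥ 8 g/dl (CTCAE Grade 2"), and section 3.1 begins the randomisation rule with "If patients develop folate deficiency concomitantly with a Hgb less than 12.0 g/dl (grade 1").

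**The concern.** The two passages cover the same patients but use different tests of recovery. Table 8 tests for 9 g/dl, and section 7.4.4.4 tests for grade 1. Between these levels lies a band in which a patient has recovered by one test and not by the other.

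Two things are at stake. First, the instructions conflict for the toxicity that the trial was set up to study. Second, olaparib interruption, dose reduction and discontinuation are secondary endpoints (section 2), and section 8.4.1 compares them by folic acid supplementation among randomised patients. In a multi-center study, the same haemoglobin course could be counted as a dose reduction at one site and a discontinuation at another, according to the passage the site follows.

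**Working it through.** No sample size or error rate is involved, so the check maps haemoglobin to the protocol's grades and then applies both rules to the same patient.

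**Step 1: grades from the protocol itself.**
- Grade 3: below 8 g/dl (Table 8).
- Grade 2: 8 to below 10 g/dl (Table 8; section 3.1 also labels below 10 as grade 2).
- Grade 1: below 12 g/dl and not grade 2, so 10 to below 12 g/dl (section 3.1).
- Grade 1 or better is therefore 10 g/dl or above.

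**Step 2: the two tests.**
- Table 8, grade 3 row: restart at a reduced dose if haemoglobin is at least 9; maximum hold 4 weeks.
- Section 7.4.4.4: applies from a 2-week hold, or with transfusion dependence; discontinue if haemoglobin is below 10 at 4 weeks.

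**Step 3: the band.** The tests disagree where haemoglobin is at least 9 and below 10, that is 9.0 to 9.9 g/dl. In time, the rules overlap from week 2, when section 7.4.4.4 begins to apply, to week 4, when Table 8's window ends.

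**Step 4: both rules, side by side**, for a patient held for grade 3 anaemia without transfusion dependence:

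| Time held | Hgb 8.5 | Hgb 9.0, 9.5 or 9.9 | Hgb 10.0 |
|---|---|---|---|
| 1 week | Table 8: hold. 7.4.4.4: not triggered | Table 8: restart, reduced. 7.4.4.4: not triggered | Table 8: restart, reduced. 7.4.4.4: not triggered |
| 2 or 3 weeks | Table 8: hold. 7.4.4.4: grade 1 not reached, limit not passed | Table 8: restart, reduced. 7.4.4.4: grade 1 not reached, limit not passed | Table 8: restart, reduced. 7.4.4.4: recovered |
| 4 weeks | Table 8: maximum hold reached, no restart. 7.4.4.4: discontinue | Table 8: restart, reduced. 7.4.4.4: discontinue | Table 8: restart, reduced. 7.4.4.4: recovered |

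Only the week 4 cell in the middle column gives opposite outcomes. Anyone still held then has passed two weeks, so section 7.4.4.4 certainly applies. At weeks 2 and 3 the middle column is unsettled: Table 8 permits a restart, while section 7.4.4.4 has a recovery level that is not yet met and a deadline that has not passed. A site that waits for grade 1 in those weeks lengthens the interruption and may carry the patient into the week 4 conflict. A site that uses 9 g/dl does not.

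**Step 5: comparison with the other blood counts.** For neutropenia, leukopenia and thrombocytopenia of grade 3 or 4, Table 9 asks for recovery to grade 1 or better within 4 weeks, which matches section 7.4.4.4. Anaemia is the exception, and no reason is given.

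**Step 6: the inequality in Table 8.** A first grade 2 occurrence needs more than 9 g/dl to restart; grade 3 needs at least 9. At exactly 9.0 g/dl the milder event has the stricter test. This is minor.

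**The case against.** The best reply is that the passages work in sequence. Table 8 is the general rule, the text beneath it refers prolonged cases onward, and the specific rule in section 7.4.4.4 then governs them. That reading is reasonable, but the text does not state it. The reference does not say that the 9 g/dl level lapses after two weeks, and Table 8's own window runs to week 4. Section 7.4.4 does not settle the matter either: for a hold beyond 4 weeks it says only that the study team is to be informed.

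A second reply is that the wording leaves room for judgement. Section 7.4.4.4 says should, not must, and section 6.1 lists situations in which patients may be discontinued. This stands, and it makes the rule less than absolute. It does not remove the conflict, because the grade 3 row of Table 8, unlike the grade 2 row, offers no investigator-judgement option.

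A third reply concerns consequence. Under section 3.1, randomised patients with folate deficiency and haemoglobin below 10 g/dl receive folic acid whatever their allocation. Those who are folate deficient and fall below 8 g/dl would generally be on folic acid in both arms before this conflict arises. This also stands. A reader might infer that the folic acid result turns on the passage each site follows; the documents do not show that.

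**Conclusion.** The contradiction is real and follows from the protocol's text and grading alone. Opposite instructions arise for a patient still held at week 4 for grade 3 anaemia with haemoglobin 9.0 to 9.9 g/dl. Weeks 2 to 3 are unsettled rather than contradictory.

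A reader might infer that every patient recovering to 9.0 to 9.9 g/dl faces opposite rules. The documents do not support that: recovery in under two weeks without transfusion dependence falls under Table 8 alone, and at weeks 2 to 3 the discontinuation deadline has not passed.

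A reader might also try to size the effect from the background section, which quotes anaemia in 37% of patients and discontinuation in 6%. On 75 patients, 75 × 0.06 = 4.5, so a few reclassified patients would look large. That does not hold up as an estimate. The 6% is discontinuation for any adverse reaction in one ovarian maintenance trial, the 37% has no grade attached, and the folic acid comparison uses only the randomised subset of the 75. The documents give no rate for grade 3 anaemia, for holds of two weeks or more, or for recovery into the band, so the number affected is unknown.

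The primary endpoint, folate deficiency within three months, is not touched. What is affected is the consistency of a safety instruction and of how secondary endpoints are recorded. That is enough to justify an amendment. This review takes no position on which recovery level is right.

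**What to change.** Reconcile Table 8 and section 7.4.4.4 so that one recovery level and one discontinuation rule apply to prolonged grade 3 anaemia. State in the text under Table 8 which passage governs once a hold reaches two weeks or transfusion dependence develops, so that weeks 2 to 3 are settled as well. As a minor item, reconcile the greater-than and at-least signs at 9 g/dl in Table 8. The medical team decides the level.

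The cost is amendment wording. No change to sample size, visits or data collection follows, since section 5.4 already has interruptions, reductions and discontinuations recorded in the eCRF.

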7.4.4.5 Management of non-haematological toxicity

Repeat dose interruptions are allowed as required, for a maximum of 4 weeks on each occasion. If the interruption is any longer than this the study monitor must be informed. Where toxicity reoccurs following re-challenge with study treatment, and where further dose interruptions are considered inadequate for management of toxicity, then the patient should be considered for dose reduction or must permanently discontinue study treatment.

Study treatment can be dose reduced to 250 mg twice daily as a first step and to 200 mg twice daily as a second step (see section 5.6 for more information on dose modification guidance). Treatment must be interrupted if any NCI-CTCAE grade 3 or 4 adverse event occurs which the investigator considers to be related to administration of study treatment.

7.4.4.6 Management of new or worsening pulmonary symptom

If new or worsening pulmonary symptoms (e.g., dyspnoea) or radiological abnormalities occur in the absence of a clear diagnosis, an interruption in study treatment dosing is recommended and further diagnostic workup (including a high resolution CT scan) should be performed to exclude pneumonitis.

Following investigation, if no evidence of abnormality is observed on CT imaging and symptoms resolve, then study treatment can be restarted, if deemed appropriate by the investigator. If significant pulmonary abnormalities are identified, these need to be discussed with the Study Physician.

7.4.4.7 Management of nausea and vomiting

Events of nausea and vomiting are known to be associated with olaparib treatment. These events are generally mild to moderate (CTCAE grade 1 or 2) severity, intermittent and manageable on continued treatment. The first onset generally occurs in the first month of treatment for nausea and within the first 6 months of treatment for vomiting. For nausea, the incidence generally plateaus at around 9 months, and for vomiting at around 6 to 7 months.

No routine prophylactic anti-emetic treatment is required at the start of study treatment, however, patients should receive appropriate anti-emetic treatment at the first onset of nausea or vomiting and as required thereafter, in accordance with local treatment practice guidelines. Alternatively, olaparib tablets can be taken with a light meal/snack (i.e. 2 pieces of toast or a couple of biscuits).

Clinical Study Protocol - 6
Olaparib - ESR-18-13807

As per international guidance on anti-emetic use in cancer patients (ESMO, NCCN), generally a single agent antiemetic should be considered eg dopamine receptor antagonist, antihistamines or dexamethasone.

7.4.4.8 Interruptions for intercurrent non-toxicity related events

Study treatment dose interruption for conditions other than toxicity resolution should be kept as short as possible. If a patient cannot restart study treatment within 4 weeks for resolution of intercurrent conditions not related to disease progression or toxicity, the case should be discussed with AZ study physician.

All dose reductions and interruptions (including any missed doses), and the reasons for the reductions/interruptions are to be recorded in the eCRF.

Study treatment should be stopped at least 3 days prior to planned surgery. After surgery study treatment can be restarted when the wound has healed. No stoppage of study treatment is required for any needle biopsy procedure.

Study treatment should be discontinued for a minimum of 3 days before a patient undergoes radiation treatment. Study treatment should be restarted within 4 weeks as long as any bone marrow toxicity has recovered.

Because the AEs related to olaparib may include asthenia, fatigue and dizziness, patients should be advised to use caution while driving or using machinery if these symptoms occur.

Table 10 Dose reductions for study treatment

Initial Dose	Following re-challenge post interruption: Dose reduction 1	Dose reduction 2
300 mg twice daily	250 mg twice daily	200 mg twice daily
250 mg twice daily	200 mg twice daily	150 mg twice daily
200 mg twice daily	150 mg twice daily	100 mg twice daily

7.4.4.9 Renal impairment

If subsequent to study entry and while still on study therapy, a patient's estimated CrCl falls below the threshold for study inclusion (≥ 51 ml/min), retesting should be performed promptly.

A dose reduction is recommended for patients who develop moderate renal impairment (calculated creatinine clearance by Cockcroft-Gault equation or based on a 24 hour urine test of between 31 and 50 ml/min) for any reason during the course of the study: the dose of olaparib *or* should be reduced to 200 mg twice daily.

Because the CrCl determination is only an estimate of renal function, in instances where the CrCl falls to between 31 and 50 mL/min, the investigator should use his or her discretion in determining whether a dose change or discontinuation of therapy is warranted.

Clinical Study Protocol - 6
Olaparib - ESR-18-13807

Olaparib has not been studied in patients with severe renal impairment (creatinine clearance ≤ 30 ml/min) or end-stage renal disease; if patients develop severe impairment or end stage disease is it recommended that olaparib be discontinued.

7.5 Biomarkers

Optional samples for biomarker research that should be collected from patients in the study where possible are the following:

- Existing paraffin embedded tissue samples from patients will be collected for assessment of folate receptors via immunohistochemical staining as according to the previously stated Exploratory Objective/Endpoint.

Unless otherwise specified in the protocol, biomarker data will not be routinely reported to sites unless specifically requested. Frequently, biomarker data are generated retrospectively towards the end of the study. Any sample material remaining after completion of analyses to fulfil the study objectives may be used for optional exploratory research to develop methods, assays, prognostics, and/or companion diagnostics related to cancer, disease process, pathways associated with disease state, PARP, and or mechanism of action of olaparib.

7.5.1 Storage, re-use and destruction of biomarker samples

Samples will be stored for a maximum of 10 years from the date of the Last Patient's Last Visit, after which they will be destroyed. The results of this biomarker research will be reported either in the CSR itself or as an addendum, or separately in a scientific report or publication. The results of this biomarker research may be pooled with biomarker data from other studies with the study drug to generate hypotheses to be tested in future research.

8. STATISTICAL CONSIDERATIONS

8.1 Statistical hypotheses

- Olaparib-treated patients develop folate deficiency
- Replacing folic acid in these patients can mitigate olaparib-induced adverse events related to its hematologic toxicity (anemia, transfusion needs/number of transfusions, dose reductions and drug discontinuation)
- Folate replacement does not affect an antineoplastic effect of olaparib

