1.2 Synopsis

Protocol Title: A study of serum folate levels in patients treated with olaparib

Rationale:

Olaparib as well as other PARP inhibitors are known to cause hematologic toxicity, most commonly, macrocytic anemia regardless of the cancer type treated. The development of anemia may lead to blood transfusions, dose reductions and delay as well as drug discontinuation¹. The cause of anemia is poorly understood. We have observed folate deficiency (<7 ng/mL) in 66% of patients treated with olaparib in a small group of patients with advanced ovarian and metastatic breast cancer occurring within weeks of treatment initiation with olaparib^{2,3}. Folate deficiency is a known cause of macrocytic anemia. However, it has not been previously reported in association with olaparib therapy. In our cohort of patients, folic acid replacement allowed us to avoid or decrease the need for blood transfusions, olaparib dose reduction and discontinuation of therapy.

Statistical methods:

[figure not shown]
A previous study by Rush investigators observed folate deficiency (<7 ng/mL) in 66% of patients treated with olaparib^{2,3}. Under this framework, a sample size of n=60 is calculated using one-sided test to have 80% power in detecting more than half (50%) of the patients having folate deficiency at 0.05 significance level. Allowing for 20% attrition, we propose a sample size of n=75 for this study. The statistical analysis will provide descriptive summaries of the primary endpoint of drug-induced folate deficiency as well the endpoint of response rate and other secondary endpoints. The significance of the observed percentage of folate-deficient cases will be assessed by statistical hypothesis test, as well as by multivariable analysis of the binary endpoint of folate deficiency adjusted by important covariates. The secondary endpoint of response rate to olaparib will be compared between the group who develop cytopenias, folate deficiency, and receive folic acid supplementation and the comparator group by descriptive summaries as well as by statistical hypothesis test. Statistical analysis will be performed in the R Statistical software. No adjustment for multiplicity will be made. Even though the sample size of 75 is optimal to achieve primary and secondary objectives, it would be reasonable to initially accrue 30 patients and re-evaluate the need for continued accrual based on the percentage of patients who develop folate deficiency in this first phase.

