8.2 Sample size determination

A previous study by Rush investigators observed folate deficiency (<7 ng/mL) in 66% of patients treated with olaparib. A sample size of $n=60$ is calculated using one-sided test to have 80% power in detecting more than half (50%) of the patients having folate deficiency at 0.05 significance level. Allowing for 20% attrition, we propose a sample size of $n=75$ for this study.

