8.4 Statistical analyses

8.4.1 Efficacy analyses

Patients will be monitored for development of anemia and folate deficiency at scheduled time points throughout the course of the study, as described in Section 1.1. Patients who develop \leq G2 cytopenias and folate deficiency will be randomly assigned in a 1:1 ratio to receive folic acid supplementation 1 mg daily or no supplementation. Patients who develop G3 or higher cytopenias and folate deficiency will be started on folic acid supplementation, thus not included in the randomization. For patients who are randomized, we will assess the impact of folic acid supplementation on anemia, need for transfusion, and dose interruption, dose reduction and drug discontinuation of olaparib as compared to those who did not receive/require folic acid supplementation. Additionally, PFS and RR to olaparib will be compared amongst randomized patients relative to folic acid supplementation.

The statistical analysis will provide descriptive summaries as well as 95% confidence intervals for the primary endpoint of drug-induced folate deficiency in addition to response rate and other secondary endpoints. Kaplan-Meier methodology will be used to estimate the PFS curve and estimate of median PFS and corresponding 95% confidence interval will be provided. The significance of the observed percentage of folate-deficient cases will be assessed by statistical hypothesis test, as well as by multivariable analysis of the binary endpoint of folate deficiency adjusted by important covariates. Covariates will include age, race/ethnic group, previous therapy, Hgb prior to olaparib therapy, genetic testing result (*BRCA* carrier status). RR and PFS will be compared to historical controls as a descriptive comparison. Analyses will be reported on the entire combined cohort of patients with solid tumors and also separately for each cancer type. The statistical analysis of the exploratory endpoint will be specified in the SAP. Statistical analysis will be performed in the R Statistical software. No adjustment for multiplicity will be made.

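### The hypothesis that folate replacement leaves olaparib's antitumour effect unchanged has no margin, power or sample size; the randomised arms are too small for a non-significant result to support it, and the aim should be restated as estimation.

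*Combined protocol and SAP*

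**What the plan says.** Section 8.1 gives three statistical hypotheses. The third is: "Folate replacement does not affect an antineoplastic effect of olaparib".

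The analysis text that bears on it is in two places:

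- **Synopsis (1.2), statistical methods.** RR is to be compared between "the group who develop cytopenias, folate deficiency, and receive folic acid supplementation and the comparator group", and this is to be done "by descriptive summaries as well as by statistical hypothesis test". The comparator group is not defined there. The secondary endpoints in Section 2 set supplemented patients against those who did not receive or did not need folic acid, which could include patients who never became deficient.
- **Section 8.4.1.** Deficient patients with qualifying cytopenias are randomised 1:1, and "PFS and RR to olaparib will be compared amongst randomized patients relative to folic acid supplementation". No test is named for this comparison. The section plans "95% confidence intervals for the primary endpoint of drug-induced folate deficiency in addition to response rate and other secondary endpoints", and a Kaplan-Meier median PFS with its own 95% CI. It does not say that any interval will be for the difference between arms.

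The only sample size is in Section 8.2 and concerns the primary endpoint. It is "calculated using one-sided test to have 80% power in detecting more than half (50%) of the patients" "having folate deficiency at 0.05 significance level", based on an earlier cohort that "observed folate deficiency (<7 ng/mL) in 66% of patients treated with olaparib". No margin for RR or PFS appears anywhere, and the plan does not say how a non-significant RR or PFS result would be interpreted.

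**The concern.** A hypothesis of no effect needs either a margin, with a trial sized to exclude losses beyond it, or an interval from which the reader can see which losses are excluded. Here there is no margin, so the only test available is a test of difference. The only outcome of such a test that could appear to support the third hypothesis is failure to reject, and in a small comparison that is likely whether or not folic acid affects response.

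What is at stake is any statement the trial makes about whether giving folic acid alongside a PARP inhibitor costs antitumour activity. Readers will look for that statement, and the plan as written gives it no adequate basis.

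**Working it through.** **1. The plan's own figure.** Inputs from 8.2: null 0.50, alternative 0.66, one-sided 0.05, power 80%. An exact binomial test with n=60, rejecting at 37 or more deficient patients, has alpha 0.046 and power 0.802. The normal approximation, [(1.645×√(0.5×0.5) + 0.842×√(0.66×0.34))/0.16]², gives 58.2, so 59. Attrition: 60/(1−0.20) = 75. The stated 60 and 75 reproduce, but they say nothing about RR or PFS.

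**2. Patients per randomised arm** (1:1, from 8.4.1), as N × deficiency rate / 2:

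- Planned rate, every deficient patient randomised: 75×0.66/2 = 24.75.
- After 20% attrition: 60×0.66/2 = 19.8.
- If only 50-75% of deficient patients fall in the Hgb window of Section 1.1, item 6 (assumption; the documents give no share): from 60×0.66×0.50/2 = 9.9 to 75×0.66×0.75/2 = 18.6.
- Arithmetic ceiling, all 75 deficient and randomised: 75/2 = 37.5.

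The count cannot be fixed more closely. Section 1.1 randomises at Hgb between 10 and 12 g/dl, against placebo. Section 8.4.1 randomises cytopenias up to grade 2, against no supplementation, and Table 8 places Hgb 8 to 10 g/dl in grade 2. These passages must be reconciled.

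**3. Precision and power for RR.** The control RR is an assumption, shown as a range of 30-60%.

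Half-width of the 95% CI for the difference, with a common RR p and n per arm: 1.96×√(2p(1−p)/n).

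Power, two-sided 0.05, for control RR p₁ against p₂ = p₁/2, with p̄ their mean: Φ{[(p₁−p₂) − 1.96√(2p̄(1−p̄)/n)] / √[(p₁(1−p₁)+p₂(1−p₂))/n]}.

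Example, 40% v 20%, n=25: (0.20 − 1.96×0.1296)/0.1265 = −0.427, and Φ(−0.427) = 0.335.

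| Control RR | Half-width, n=25 | Power for halving, n=20 | n=25 | n=37 |
|---|---|---|---|---|
| 30% | 0.254 | 0.201 | 0.242 | 0.337 |
| 40% | 0.272 | 0.276 | 0.335 | 0.466 |
| 50% | 0.277 | 0.368 | 0.445 | 0.607 |
| 60% | 0.272 | 0.478 | 0.572 | 0.747 |

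At 20 per arm the half-width is 0.284 to 0.310. At 25 per arm, a true halving would be non-significant with probability 0.758, 0.665, 0.555 and 0.428 down the table.

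**4. PFS.** No event count is given, and Section 3.4 ends the study 7 months from enrolment. With 20 to 40 events (assumption), power is 15-25% for a hazard ratio of 1.5 and 34-59% for 2.0. The 95% limits lie a factor exp(1.96×2/√events) either side of the estimate: 2.40 at 20 events, 1.86 at 40.

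**5. Could a margin be added instead?** With equal true RR of 30-60%, one-sided 0.025 and 80% power, an illustrative 20-point margin needs 83-99 per arm and a 30-point margin 37-44. For PFS, an illustrative hazard-ratio margin of 1.5 needs 191 events and 2.0 needs 66. None of these is within reach of about 50 randomised patients.

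**6. Features that push towards no difference or lower precision.** Under Section 3.1, randomised patients whose Hgb falls below 10 g/dl with folate deficiency receive folic acid whatever their allocation, which pulls the arms together. Non-measurable disease is eligible (4.1, item 9), so fewer patients may be evaluable for response. If accrual stopped at the 30-patient review in 8.5, the arms would hold about 30×0.66/2 = 9.9 each.

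**The case against.** The case for the plan has real substance. Section 3.1 calls the study a pilot, RR and PFS are secondary, and the objectives in Section 2 are neutral: they speak of assessing RR and PFS in relation to folate and supplementation. The bullets in 8.1 read more like research propositions than test specifications. Section 8.4.1 already plans 95% CIs for RR and for median PFS.

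Four stronger readings are tempting, and the documents do not support them:

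- **That a non-significant result will be reported as no harm.** No passage says so. The plan is silent on interpretation, which is a gap and not a stated intention.
- **That both endpoints will be judged by difference tests between the randomised arms.** A test is explicit only for RR, only in the synopsis, and against an undefined group. For PFS the text says no more than that it will be compared. If the comparator took in non-deficient patients, an illustrative 25 v 50 split would give about 40% power for 40% v 20%, still low.
- **That 25 per arm is a maximum.** It is an expected count at a 66% rate; the ceiling is about 37.
- **That a halving of response would usually be missed.** This depends on the control RR. At 25 per arm, power for a halving rises from 24% at RR 30% to 71% at RR 70%.

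What remains of the objection softens the point without removing it. Intervals for each arm's RR or median PFS are not intervals for the difference, and nothing connects them to the third hypothesis. Pilot status argues for estimation, not for listing a hypothesis of no effect.

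**Conclusion.** The point holds in this form: 8.1 lists a no-effect hypothesis that has no margin, power or sample size behind it, and the planned RR and PFS comparisons cannot support it through a non-significant result. At about 25 per arm and an assumed control RR of 30-60%, even an observed difference of zero would leave RR losses of about 25-28 points unexcluded.

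The size rests on the 66% deficiency rate, on every deficient patient being randomised, and on the assumed control RR. Attrition and the Hgb window make the arms smaller, and controls moving to folic acid would dilute any difference. A deficiency rate above 66% would help only in part: at the ceiling of about 37 per arm, power for 40% v 20% is still 47%.

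It should be corrected before analysis, but it does not touch the primary endpoint, whose sample size reproduces.

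**What to change.** - **Section 8.1, third bullet:** restate the aim as estimating the RR difference and the PFS hazard ratio between the randomised arms, each with a 95% CI, analysed as randomised.
- **Synopsis:** name the randomised arms as the comparison for RR, in place of the undefined comparator group.
- **Section 8.4.1:** specify the interval for the between-arm difference. State that a non-significant test will not be read as absence of effect, and that the conclusion will say which losses the CI excludes. State the time origin for the hazard ratio, since 7.1.1 counts PFS from enrolment and patients are randomised later.

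No extra patients, visits or procedures are needed. The cost is a weaker stated claim and one added estimate, the PFS hazard ratio, which will be imprecise with 7 months of follow-up. If the sponsor wants to keep a no-effect claim, it would have to pre-specify a margin and size the trial for it.
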